5.3.4. Death

Any death of a research subject that is possibly, probably or definitely related to the research must be reported within 24 hours of an investigator becoming aware of the death.

5.3.5. New Information

New information that might affect the willingness of a subject to enroll or remain in the study should be reported within 7 calendar days of an investigator first becoming aware.

5.3.6. Suspension or Termination of Research Activities

Any suspension or termination of research activities, including holds on new enrollment, placed upon the research by the study sponsor, NIH or IC leadership, or any regulatory agency must be reported within 7 calendar days of an investigator becoming aware.

5.3.7. Expedited Reporting to the IRB

Death related to research must be reported within **24 hours**.

The following will be reported within **7 calendar days** of investigator awareness:

- Actual or suspected UPs;
- Actual or suspected non-compliance;
- Actual or suspected Major PDs;
- SAEs that are actual or suspected UPs;

- New information that might affect the willingness of a subject to enroll or remain in the study;
- Suspension or termination of research activities, including holds on new enrollment, placed upon the research by the study sponsor, NIH or IC leadership, or any regulatory agency..

5.3.8. Annual Reporting to the NIAID IRB

The following will be reported to the IRB in summary at the time of Continuing Review:

- Summary of UPs and non-compliance;
- AEs, including SAEs, that are not UPs, as a narrative summary statement indicating whether these events were within the expected range;
- Minor PDs (aggregate summary);
- Any trends or events which in the opinion of the investigator should be reported.

6. STATISTICAL CONSIDERATIONS AND SAMPLE ANALYSIS

6.1. Overview

This is a dose-escalation study to evaluate the safety and immunogenicity of a 2-dose regimen with the DS-Cav1 vaccine given alone or with adjuvant. As available, the effect of a 1-dose regimen will also be evaluated in up to 5 subjects in each group who will be offered the option to receive only a single administration of the study product. The primary objectives relate to safety and tolerability; the secondary and exploratory objectives relate to immunogenicity and durability of immune responses.

6.2. Endpoints

6.2.1. Primary Endpoints: Safety

Assessment of product safety will include clinical observation and monitoring of hematological and chemical parameters. Reactogenicity will be closely monitored for 7 days after each product administration and safety evaluated by clinical visits through the study duration.

The following parameters will be assessed:

- Local reactogenicity signs and symptoms
- Systemic reactogenicity signs and symptoms
- Laboratory measures of safety
- Adverse events
- Serious adverse events
- New chronic medical conditions

6.2.2. Secondary Endpoints: Immunogenicity

The principal immunogenicity endpoints are antigen-specific antibody responses as evaluated by neutralization assays. The primary timepoints for immunogenicity evaluation are 2 and/or 4 weeks after the first injection for each group. Immunogenicity after the second injection will also be evaluated when applicable.

6.2.3. Exploratory Endpoints

ELISA, neutralization assay, and T cell assays performed with research samples collected at study timepoints as well as other immunogenicity assays throughout the study may be completed as exploratory evaluations.

6.3. Sample Size and Accrual

The study design is to have 90 healthy adult subjects divided equally among 6 groups.

6.3.1. Power Calculations for Evaluation of Safety

The goal of the safety evaluation for this study is to identify safety concerns associated with injections of the investigational vaccine. Primary sample size calculations for safety are expressed in terms of the ability to detect serious adverse experiences.

Table 2 describes the probability of observing 0 and 2 or more adverse events among 10, 15, 30, and 90 subjects, based on a range of true underlying probabilities. For example, if an adverse event of interest has a true incidence rate of 1%, there is an 86% chance that we won't see any events in a group of 15 participants. However, if this same 1% incidence applies to all 90 participants in the study, there is a 60% (100-40%) chance of observing at least one occurrence and a 23% chance of observing 2 or more.

Table 2: Probability of Observing Adverse Events

Probability of Adverse Event	Prob. 0/10	Prob. 2+/10	Prob. 0/15	Prob. 2+/15	Prob. 0/30	Prob. 2+/30	Prob. 0/90	Prob. 2+/90
0.01	0.90	<0.01	0.86	0.01	0.74	0.04	0.40	0.23
0.05	0.60	0.09	0.46	0.17	0.21	0.45	0.01	0.94
0.10	0.35	0.26	0.21	0.45	0.04	0.82	<0.01	>0.99

If we do not observe any AEs in a group of 10 (for example, at the dose escalation review), the upper 95% confidence interval for the true incidence rate at that dose is 31%; that is, we can be reasonably confident that the true rate is no more than 31%. If we do not observe any of a specific type of adverse events in a specific arm (n=15), the upper bound of a 95% confidence interval for the true incidence is 21.8%. Similarly, if we do not observe any of a specific type of

adverse events in a pair of arms (such as 1 & 2; n=30), the upper bound of a 95% confidence interval for the true incidence is 12%.

6.3.2. Power Calculations for Evaluation of Immunogenicity

Although immunogenicity is a secondary endpoint, it is of sufficient interest that we briefly present the power to detect a difference between immune responses before and after the first dose, and between two dose cohorts. Based on previous research[44], we expect the ELISA and neutralization results to be approximately normally distributed on the \log_{10} scale, with standard deviation approximately 0.2-0.5 \log_{10} . Using the conservative value of 0.5 \log_{10} for the true standard deviation, we will have good power (90% or better) to detect a difference in the magnitude of the immune response of approximately .45 \log_{10} with 15 per group. With 30 per group, we will be able to detect a difference in the average magnitude of approximately 0.3 \log_{10} .

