4. STUDY DESIGN AND CLINICAL PROCEDURES

This is an open-label, dose-escalation study to examine the safety, tolerability and dose of the DS-Cav1 vaccine alone or with adjuvant in healthy adults. A vaccine regimen of DS-Cav1 as a prime followed 12 weeks later with a DS-Cav1 boost will be compared to a vaccine regimen of an adjuvanted DS-Cav1 prime followed 12 weeks later with an adjuvanted DS-Cav1 boost for each dose level. The last 5 subjects enrolled in each group will be offered the option not to receive the boost at Week 12, such that immunogenicity of a single vaccine dose can be evaluated. The hypotheses are that the vaccine will be safe and tolerable for human administration and will induce detectable immune responses. The primary objective is to evaluate the safety and tolerability in healthy adults of the investigational vaccine alone and with adjuvant. Secondary objectives are related to the immunogenicity of the vaccine alone and with adjuvant. The study schema is shown in [Table 1](#).

Table 1: VRC 317 Study Schema

VRC 317 Study Schema				
Group	Subjects	Dose	Day 0	Week 12 ^[1]
1	15	50 mcg	DS-Cav1	DS-Cav1
2	15		DS-Cav1 + alum	DS-Cav1 + alum
3	15	150 mcg	DS-Cav1	DS-Cav1
4	15		DS-Cav1 + alum	DS-Cav1 + alum
5	15	500 mcg	DS-Cav1	DS-Cav1
6	15		DS-Cav1 + alum	DS-Cav1 + alum
Total	90*	All DS-Cav1 vaccinations are administered with needle and syringe into the deltoid muscle. *Up to 100 subjects may be enrolled if needed to evaluate safety or immunogenicity. [1] This dose is optional for the last 5 subjects enrolled in each group that receive the Day 0 injection and any additional subjects enrolled to evaluate safety or immunogenicity.		

The study will be conducted at the VRC Vaccine Evaluation Clinic (VEC) in the NIH Clinical Center (NIH CC). The visit schedule is shown in Appendix III. The expected duration of time on study per subject is approximately 44 weeks.

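### The 90% immunogenicity power in Section 6.3.2 fits a paired comparison; between two dose cohorts the same inputs give about 60–66%

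*Combined protocol and SAP*

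**What the plan says.** Section 6.3.2 announces "the power to detect a difference between immune responses before and after the first dose, and between two dose cohorts". It expects ELISA and neutralization results to be roughly normal on the log10 scale with "standard deviation approximately 0.2-0.5" log10. The power statement adopts the upper end of that range ("Using the conservative value of 0.5" log10). For groups of 15 it then says "we will have good power (90% or better) to detect a difference in the magnitude of the immune response of approximately .45", in log10 units. For the larger size it reads "With 30 per group, we will be able to detect a difference in the average magnitude of approximately 0.3", in the same units. The section names no test, alpha or sidedness, and gives no separate figure for the between-cohort case.

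Section 6.4.3 plans within-subject comparisons around each dose, and between-subject comparisons of dose cohorts and of alum with no alum. It names the Wilcoxon rank sum test, a test for two independent samples, for the primary comparisons at 2 and/or 4 weeks after the first dose. Section 6.4 applies no multiplicity adjustment. Section 6.3 has six equal groups totalling 90 subjects, so 15 is one group and 30 is a pair of groups. Section 4 adds: "The last 5 subjects enrolled in each group will be offered the option not to receive the boost at Week 12".

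**The concern.** A within-subject change and a difference between two independent groups have different standard errors. With n subjects per group and SD s, the first is s_change/√n and the second is s√(2/n). One detectable difference can serve both only if s_change equals s√2, which means uncorrelated pre- and post-dose values. Section 6.3.2 uses one figure for both and gives 0.5 as the SD of the assay results, not of a change. The phrase 'per group' also invites the between-group reading.

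What is at stake is how the dose and alum comparisons are read. Someone relying on Section 6.3.2 would take a non-significant result between two groups of 15 as good evidence against a 0.45 log10 (10^0.45 = 2.8-fold) difference. Section 6.4.5 lets interim immunogenicity results inform later decisions and be published, so the misreading could travel beyond the final report.

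**Working it through.** **Inputs.** SD 0.5 log10, differences 0.45 and 0.3 log10, and 15 and 30 per group (Section 6.3.2); rank sum test (Section 6.4.3). Assumed, because not stated: two-sided alpha 0.05. One-sided 0.05 is tried as well.

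**Step 1: reproduce the plan's figures.** One-sample (paired) t-test, SD of the change 0.5, noncentrality d√n/0.5 on n − 1 degrees of freedom.
- n = 15, d = 0.45: 0.45 × √15 / 0.5 = 3.49; critical t 2.145; power 89.9%.
- n = 30, d = 0.3: 0.3 × √30 / 0.5 = 3.29; critical t 2.045; power 88.8%.
- Solving for 90% power gives 0.450 at n = 15 and 0.306 at n = 30, which match the stated .45 and 0.3.

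**Step 2: the between-cohort comparison with the same inputs.** Two-sample t-test, noncentrality d / (0.5√(2/n)) on 2n − 2 degrees of freedom.
- n = 15, d = 0.45: standard error 0.5 × √(2/15) = 0.183; 0.45/0.183 = 2.46; critical t 2.048; power 66%.
- n = 30, d = 0.3: standard error 0.5 × √(2/30) = 0.129; 0.3/0.129 = 2.32; critical t 2.002; power 63%.
- Rank sum test, simulated on normal data (20,000 trials): about 63% and 60%.

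**Step 3: what 90% power requires between groups** (two-sample t, SD 0.5, two-sided 5%).

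| Comparison | Detectable difference, log10 | Fold |
|---|---|---|
| 15 v 15 | 0.61 | 4.1 |
| 30 v 30 | 0.43 | 2.7 |
| 45 v 45 (alum v none, doses pooled) | 0.35 | 2.2 |
| 10 v 10 (after second injection, if all five optional boosts in each group are declined) | 0.77 | 5.8 |

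Reaching 90% for 0.45 and 0.3 log10 would need 27 and 60 per group.

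**Step 4: can another reading recover the stated figures between groups?**
- One-sided 5%: power is 78% (n = 15) and 74% (n = 30). The 90% detectable difference at n = 15 is 0.55.
- 80% power instead of 90%: 0.53 at n = 15, still above 0.45.
- Actual enrolment: Section 1.3 reports 95 subjects, about 16 per group (95/6). Two-sample t power for 0.45 at 16 per group is 69%.
- A smaller SD: 90% needs an SD of at most about 0.37 (n = 15) or 0.35 (n = 30). The section says it uses 0.5.

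**Step 5: the paired reading.** If 0.5 is the SD of a single titre, the SD of the change is 0.5√(2(1 − ρ)), where ρ is the pre/post correlation. It equals 0.5 only at ρ = 0.5. Paired power for the two cases is 63% and 61% at ρ = 0, 75% and 74% at ρ = 0.25, and over 99% at ρ = 0.75. The plan states neither ρ nor the SD of the change.

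**The case against.** The strongest case on the other side concerns weight rather than arithmetic. Immunogenicity is secondary, the sample size rests on safety (Section 6.3.1), and enrolment had reached 95 with all escalation steps complete. Correcting the paragraph changes no enrolment or escalation decision. Nor does any section plan to claim equivalence from a non-significant test. This stands, and it is why the remedy is a restatement and not a larger trial.

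The shortfall also depends on the SD. At 0.35, inside the stated range, two-sample t power is 92% and 90%; at 0.3 it is 98% and 97%. The baseline-adjusted regression in Section 6.4.3 would reach about 90% at SD 0.5 if the pre/post correlation were near 0.7. Both points limit the practical loss. But the sentence fixes the SD at 0.5, and the regression is only to be explored.

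The one-sample origin is an inference, since no formula is named. The match at both sample sizes is close, and the between-group shortfall does not depend on the inference. Finally, Section 6.3.2 makes no power claim after the second injection, so the 10 v 10 figure is a conditional worst case that adds information and does not correct a stated number.

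**Conclusion.** The power statement is wrong as written for comparisons between dose cohorts. Under its own SD of 0.5 log10, and assuming two-sided 5%, power is 66% for 0.45 log10 at 15 per group and 63% for 0.3 log10 at 30 per group by t-test, or about 63% and 60% by the planned rank sum test, against a stated 90% or better. One-sided testing does not close the gap. The stated differences are right to within rounding for within-subject change, provided the SD of that change is 0.5; the plan should say so. The finding assumes roughly normal log10 titres with equal SD in the groups, as the section itself does, and complete data; any missing samples would lower power further.

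**What to change.** Rewrite the paragraph in Section 6.3.2:
- Name the test, alpha and sidedness for each type of comparison.
- Between groups, at SD 0.5 and 90% power: about 0.61 log10 for 15 v 15 and 0.43 log10 for 30 v 30. Add 0.35 log10 for 45 v 45 if the pooled alum comparison is to be described.
- Confine .45 and 0.3 log10 to within-subject change, and state that 0.5 is then the SD of the change (a pre/post correlation of 0.5 if each titre has SD 0.5).
- Either base the figures on the rank sum test or note that they are t-test figures and that the rank sum test needs a slightly larger difference, roughly 0.02 log10 more at 15 or 30 per group. That allowance should not be carried over to 10 per group.
- If comparisons after the second injection are to be described, note that as few as 10 per group may contribute, with about 0.77 log10 detectable.
- Giving the same figures at an SD of 0.35 would show how far the conclusion depends on the SD.

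The cost is one paragraph of text and less favourable stated differences. The sample size does not change.

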6.4. Statistical Analysis

Since enrollment is concurrent with receiving the first study vaccination, the expectation is that all participants will receive at least one vaccination and therefore will provide some safety data. All statistical analyses will be performed using statistical software R. No formal multiple comparison adjustments will be employed for safety endpoints or immunogenicity endpoints.

6.4.1. Baseline Demographics

Baseline characteristics including demographics and laboratory measurements will be summarized using descriptive statistics.

6.4.2. Safety Analysis

Reactogenicity: The number and percentage of subjects experiencing each type of reactogenicity sign or symptom will be tabulated by severity. For a given sign or symptom, each subject's reactogenicity will be counted once under the maximum severity for all assessments.

Adverse Events: AEs will be coded into Medical Dictionary for Regulatory Activities (MedDRA) preferred terms. The number and percentage of subjects experiencing each specific AE will be tabulated by severity and relationship to study product. For the calculations in these tables, each subject's AE will be counted once under the maximum severity or strongest recorded causal relationship to treatment.

A complete listing of AEs for each subject will provide details including severity, relationship to treatment, onset, duration and outcome.

Safety Laboratory Values: Boxplots of local laboratory values will be generated for baseline values and for values measured during the course of the study. Each boxplot will show the 1st quartile, the median, and the 3rd quartile. Outliers, or values outside the boxplot, will also be plotted. If appropriate, horizontal lines representing boundaries for abnormal values will be plotted.

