3. STUDY OBJECTIVES

3.1. Primary Objectives

- To evaluate the safety and tolerability of DS-Cav1 alone or with adjuvant when administered IM at a dose of 50 mcg to healthy adults.
- To evaluate the safety and tolerability of DS-Cav1 alone or with adjuvant when administered IM at a dose of 150 mcg to healthy adults.
- To evaluate the safety and tolerability of DS-Cav1 alone or with adjuvant when administered IM at a dose of 500 mcg to healthy adults.

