4.4.1. Discontinuation from Study Injections

A subject may be discontinued from study injections for the following reasons:

- Pregnancy;
- Grade 3 AE assessed as related to study product (except that self-limited Grade 3 solicited reactogenicity does not require discontinuation of injections);
- Grade 4 AE assessed as related to study product;
- Immediate hypersensitivity reaction associated with study product;
- Intercurrent illness that is not expected to resolve before the next scheduled injection;
- Treatment with systemic glucocorticoids (e.g., prednisone or other glucocorticoid) or other immunomodulators (other than nonsteroidal anti-inflammatory drugs [NSAIDs]), with the exception that study injection may continue per PI discretion if the next one occurs at least 2 weeks following completion of glucocorticoid treatment; or,
- The PI assesses that it is not in the best interest of the subject to continue receiving study product.

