4.5. Criteria for Pausing and Resuming the Study

4.5.1. Criteria for Pausing the Study

The PI and PSRT will closely monitor and analyze study data as they become available and will make determinations regarding the presence and severity of AEs. Enrollments and administration of study product will be paused by the PI, and the IND Sponsor will be promptly notified, according to the following criteria:

- **One** (or more) subject experiences a **Serious Adverse Event (SAE)** assessed as related to study product.
- **Two** (or more) subjects experience the same **Grade 3 or higher unsolicited AE** assessed as related to the study product.

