5. SAFETY AND ADVERSE EVENTS

5.1. Adverse Events

An adverse event (AE) is any untoward or unfavorable medical occurrence in a human subject, including any abnormal sign (e.g., abnormal physical exam or laboratory finding), symptom, or disease temporally associated with the use of study treatment, whether or not considered related to the study treatment.

AEs will be graded according to the Table for Grading Severity of AEs ([Appendix IV](#)). The following guidelines will be used to determine if an AE should be recorded in the database:

- Solicited AEs (i.e. reactogenicity parameters) will be recorded in the study database for 7 days after each study injection without the collection of product attribution assessments.

Clinicians will follow and collect resolution information for any reactogenicity symptoms that are not resolved within 7 days.

- Unsolicited AEs will be recorded in the study database from the date of receipt of each study injection through the visit scheduled at 28 days after each injection with the collection of product attribution assessments. At other time periods between injections and when greater than 28 days after the last injection, only SAEs (as detailed in [Section 5.2](#)) and new chronic medical conditions will be recorded as an AE through the last study visit.

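### As written, the Section 6.4.2 reactogenicity table merges both injections, although up to 5 of 15 subjects per group (and any additional subjects) may receive only one

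*Combined protocol and SAP*

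**What the plan says.** The primary objectives (Section 3.1) are set by dose level, alone or with adjuvant. The first reads "To evaluate the safety and tolerability of DS-Cav1 alone or with adjuvant when administered IM at a dose of 50 mcg to healthy adults", and the other two repeat it for 150 and 500 mcg. Section 6.2.1 lists local and systemic reactogenicity among the primary safety parameters.

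Section 6.4.2 tabulates subjects with each sign or symptom by severity. For a given symptom, each subject's "reactogenicity will be counted once under the maximum severity for all assessments". It names no split by injection or group and gives no denominator rule.

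Exposure differs between subjects. Section 4 states: "The last 5 subjects enrolled in each group will be offered the option not to receive the boost at Week 12". The footnote to Table 1 extends the option to any additional subjects, within a cap of 100. Section 6.1 adds that, as available, "the effect of a 1-dose regimen will also be evaluated in up to 5 subjects in each group".

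Under Section 5.1, solicited events are "recorded in the study database for 7 days after each study injection without the collection of product attribution assessments". The data therefore exist injection by injection.

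**The concern.** A count at the maximum over both injections is an ever-reacted rate. It raises two difficulties for a tolerability endpoint.

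- **Timing is lost.** Whether reactions follow the first or the second injection is basic information for a two-injection vaccine, and the merged line removes it.
- **Exposure is mixed.** Subjects with one diary period and subjects with two enter the same percentage, in a proportion set partly by subject choice. That percentage describes neither a one-injection nor a two-injection course.

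The plan is more careful with its secondary endpoint. Section 6.4.3 names comparisons before and after the first dose, before and after the second, between dose cohorts, and with versus without alum. The primary tolerability parameters get no such specification.

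**Working it through.** **Inputs.** 15 subjects per group (Section 6.3). The second injection is optional for the last 5 (Section 4), so with no other losses the second-injection denominator is 10 to 15. Reaction counts and rates below are assumed for illustration; the documents give none.

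**1. The plan's own figure.** For a single arm of 15 with no events, Section 6.3.1 states that "the upper bound of a 95% confidence interval for the true incidence is 21.8" percent. The exact two-sided bound is 1 − 0.025^(1/n):

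- n=15: 1 − 0.025^(1/15) = 21.8%, which matches.
- n=10: 30.8% (plan: 31%).
- n=30: 11.6% (plan: 12%).

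The plan's precision figures reproduce and are not in dispute.

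**2. One table line, two opposite profiles.** Take Grade 3 of one symptom, 15 subjects, 10 given the second injection.

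| | After injection 1 | After injection 2 | Line under 6.4.2 |
|---|---|---|---|
| Group A | 3/15 = 20% (95% CI 4.3 to 48.1) | 0/10 (upper bound 30.8%) | 3/15 = 20% |
| Group B | 0/15 (upper bound 21.8%) | 3/10 = 30% (95% CI 6.7 to 65.2) | 3/15 = 20% |

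This needs no assumption about correlation within subjects. Nor does the loss of timing depend on the optional boost: with all 15 boosted, 3/15 then 0/15 and 0/15 then 3/15 also both read 20%. The optional boost adds the wrong denominator, since 3 reactors among 10 injected appear as 3/15.

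**3. How far uptake alone moves the merged rate.** Assume the same rate q after each injection.

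- Independent reactions, all 15 boosted: 1 − (1 − q)².
- Independent reactions, 10 of 15 boosted: [10 × (1 − (1 − q)²) + 5q] / 15.
- Perfectly correlated reactions: q in both cases.

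| q | 15 boosted | 10 boosted | Gap, independent | Gap, perfectly correlated |
|---|---|---|---|---|
| 10% | 19.0% | 16.0% | 3.0 points | 0 |
| 20% | 36.0% | 30.7% | 5.3 points | 0 |
| 30% | 51.0% | 44.0% | 7.0 points | 0 |
| 50% | 75.0% | 66.7% | 8.3 points | 0 |

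At q = 10% the gap is 0.03 × 15 = 0.45 of one subject. With unequal assumed rates, 5% then 30%, independence gives 1 − 0.95 × 0.70 = 33.5% with 15 boosted and (10 × 0.335 + 5 × 0.05)/15 = 24.0% with 10. These figures show direction and possible size only.

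**4. Precision after the change.** With no events, the bound after injection 1 stays at 21.8%. After injection 2 it is 21.8% at n=15, 23.2% at 14, 24.7% at 13, 26.5% at 12, 28.5% at 11 and 30.8% at 10.

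**The case against.** **The counting phrase can be read otherwise.** Diaries are filled in daily for 7 days, and Section 6.2.1 describes monitoring after each administration. The phrase could therefore mean the maximum over daily readings within one injection. That is possible, but Section 6.4.2 sets no such limit and gives no per-injection denominator. If that reading is intended, the fix only writes it down.

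**The group split is implied.** This stands. Section 3.1 sets objectives by dose, alone or with adjuvant, and Section 6.3.1 gives precision per arm and per pair of arms. A reader might infer that the six groups would be pooled because 6.4.2 does not name them; the documents do not support that.

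**The uptake effect is hypothetical.** This also stands. At equal rates it is zero under perfect correlation, and at a 10% rate it is small beside intervals as wide as 4.3 to 48.1%. The case rests on step 2 of the working, not on step 3.

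**Solicited reactions are reviewed elsewhere.** A reader might infer that tolerability hangs on this table because Section 4.5.1 pauses the study only for a related SAE or when two or more "subjects experience the same Grade 3 or higher unsolicited AE assessed as related to the study product", and because Section 4.4.1 has the proviso "except that self-limited Grade 3 solicited reactogenicity does not require discontinuation of injections". That does not follow. A pause rule is not an analysis and has no bearing on tabulation. The Protocol Safety Review Team also sees first-injection follow-up at the Section 4.3 reviews and safety summaries weekly (Section 8.8.1). Nor does Section 1.3 infer tolerability from the absence of pauses, since it reports that team's own favourable assessment. These reviews guide conduct, however; they are not the endpoint analysis.

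**One-dose tolerability is not a stated objective.** Correct. Section 4 gives single-dose immunogenicity as the reason for the option. This argues against a separate table of one-injection subjects, who would number about 5 per group (zero-event bound 1 − 0.025^(1/5) = 52.2%) and be defined by a choice made after the first injection. It does not argue against tabulating by injection.

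**Conclusion.** The point holds as one about how a primary endpoint is tabulated. Read as written, Section 6.4.2 merges two injections that not all subjects receive, so one percentage can describe opposite reactogenicity profiles. In the example, 20% stands for a first-injection rate of 20% or 0%, and a second-injection rate of 0% or 30%.

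This rests on the natural reading of the counting phrase, and on the optional second injection being declined by some subjects for the exposure-mixing part. A reader might infer that subjects with strong first reactions decline the second injection and so bias the table. The documents contain nothing on reasons for declining, so no such bias is claimed.

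Section 6.4.3 mentions a Statistical Analysis Plan, but only for immunogenicity cohorts, and no separate text is available here. If it already sets out per-injection tables, a cross-reference in 6.4.2 is enough. No safety decision or hypothesis test depends on the outcome.

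**What to change.** In Section 6.4.2, replace the counting rule with wording to this effect: *Reactogenicity will be tabulated by group (1 to 6), separately after injection 1 and after injection 2. The denominator is the number of subjects in the group who received that injection, and each subject is counted once per symptom at the maximum severity recorded for that injection. A summary over any injection will be given as a supplement.*

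The cost is longer tables (6 groups × 2 injections) and second-injection denominators that may fall to 10 per group. No new data, visits or thresholds are needed. The change can be made with enrolment already at 95, because it reorganises records already kept for each injection.

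One clerical correction can be made at the same time: Section 4.3 points to Section 4.4 for the pause criteria, which are in Section 4.5.
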